2.2.2 Secondary objectives

Secondary objectives are to determine if oral prolonged release melatonin can:

- 1. reduce delirium severity and duration for those who develop a delirium episode;
- 2. reduce delirium incidence;
- 3. cause adverse effects, in particular sedation;
- 4. positively influence adverse events associated with delirium episodes, including:
 - vi. length of hospital stay and inpatient resource utilisation;
 - vii. benzodiazepine and antipsychotic use (delirium or non-delirium indication);
 - viii. in-hospital complications (pressure areas, falls, thromboembolism, pneumonia, functional decline);
 - ix. days spent in coma and survival;
 - x. Patient and family distress;
- 5. provide other symptom benefits in the form of improved sleep quality.

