5.0 INTERVENTIONS

5.1 Study medication

Arm 1: Oral melatonin prolonged release 2mg (Neurim Pharmaceuticals Ltd) taken at 2000 +/-hours. Intervention will be commenced within 48 hours of admission and continued until delirium occurrence, discharge or for a maximum of three weeks if patient remains in hospital (e.g. while awaiting long-term care placement) after any acute medical issues imparting a delirium risk have been resolved.

Arm 2: Oral placebo tablet containing identical ingredients except the active ingredient melatonin

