6.2 Secondary outcomes

The secondary endpoints provide a profile of delirium risk and precipitants, measure toxicities, inform the health economic analysis; and explore the collateral benefits in sleep. The severity and duration of delirium, and its impacts will be evaluated if it occurs. Days in coma will also be measured as this may occur in severe irreversible delirium prior to death. Sleep quality will require participant involvement, measured every five days only to minimize participant burden.

Delirium profile: DRS-R-98 cut off score ≥17.75 will diagnose delirium and as a continuous variable will assess severity.

Toxicity: Sedation will be rated daily by observation using the Richmond Agitation-Sedation Scale - Palliative (RASS - Pal). This has modified the intensity of verbal or physical stimuli required to avoid additional discomfort in the palliative population, and has good correlation with the original RASS (interclass correlation coefficient 0.83 – 0.98). It is 10-point scale using observation, verbal stimulation, and physical stimulation, differentiating between different potency of stimulation (verbal versus physical), and also examines constructs related to delirium (agitation, sedation, inattention as measured by eye contact). It will also assess days in coma defined as RASS-Pal score of -4 or -5. Other adverse effects will be assessed using the National Cancer Institute Common Terminology Criteria.

Benzodiazepine and antipsychotic use: regular use and administration of 'as required' doses of all benzodiazepine and antipsychotics will be recorded daily, including the clinical indication. This will capture whether there is a reduced need for nocturnal sedation due to concurrent melatonin use and benzodiazepines/antipsychotic administration for delirium symptoms.

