Delirium risk factors: will be recorded at baseline: age (>65 and >80 years of interest), cognitive impairment defined as SBT score >4, visual impairment, presence of infection, and use of physical restraint. Risk factors which have uncertain/contradictory evidence will also be collected to advance the science for future work: primary or secondary brain malignancy, benzodiazepines (oral diazepam equivalents), corticosteroids (oral dexamethasone equivalents), opioids (oral morphine equivalents), hearing impairment, comorbidities (Charlson Comorbidity Index), diagnosis of depression, use of indwelling bladder catheter, number of room/bed changes during admission, multiple medications (number of medications), and high blood urea/creatinine ratio (>18).

Delirium precipitating factors: The Delirium Etiology Checklist (DEC) will be completed at time of delirium occurrence. The DEC is a structured tool that utilizes clinical information from all sources, and then applies a weighted approach to each category of potential delirium precipitants.³ Each category is rated as ruled out (0), present and apparently not contributory (1), present and possibly contributory (2), likely cause (3), or definite cause (4). It can document multiple concurrent causes.

In-hospital complications: Falls, pneumonia, thromboembolism, pressure areas, changes in performance status (AKPS⁶¹) and survival will be documented, complications which increase if delirium occurs.

Family distress (Delirium experience questionnaire): The Delirium Experience Questionnaire is a face-valid, brief instrument that assesses recall of the delirium experience and distress related to the delirium episode in patients, spouses/caregivers, and nurses, and has been used in cancer patients.²⁴

Sleep quality: will be measured using the Insomnia Severity Index at baseline and every 5 days during the admission, which has established psychometric properties in cancer. The ISI is a 7-item scale that characterizes the type of sleep problem (difficulty falling asleep, staying asleep or waking up too early), and assesses impact (sleep satisfaction, associated distress and impact on others).

Inpatient resource utilisation: variables include duration of admission (days), daily medications, investigations (blood tests, imaging, urine cultures), and level of nursing required for transfers or care (independent, standby assistance, one or two assistants) and use of one to one nursing (hours).

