The delirium etiology checklist (DEC) will be completed at time of incident delirium, in conjunction with the participants treating physician. The DEC is a structured tool that utilizes clinical information from all sources, and then applies a weighted approach to each category of potential delirium precipitants.³ Each category is rated by treating physician as ruled out (0), present and apparently not contributory (1), present and possibly contributory (2), likely cause (3), and definite cause (4). It can document multiple concurrent causes of delirium, which is important in cancer patients where the average number of precipitants is 3 or more.¹⁵ This checklist will also be completed during the study period if new precipitants are identified. Day of resolution of prior precipitant will also be recorded. If a new potential precipitating factor occurs after day 7 of the study period the DRS-R-98 will be readministered.

7.8.4 Sleep quality:

Sleep quality will be measured using the Insomnia Severity Index (ISI) at every 5 days during admission, which has established psychometric properties in cancer. The ISI is a 7 item scale which characterizes the type of sleep problem (difficulty falling asleep, staying asleep or waking up too early), and assesses impact (sleep satisfaction, associated distress and impact on others).⁵ The psychometric properties of the ISI in cancer patients are well established, with a cut-off of 8 having optimal sensitivity and specificity.

7.8.5 Inpatient resource utilization:

Variables include duration of admission (days), daily medications, investigations (blood tests, imaging, urine cultures), and level of nursing required for transfers or care (independent, standby assistance, one or two assistants) and use of one to one nursing (hours).

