8.0 STUDY PROCEDURES

8.1 Table of study measures

	Eligibility	Baseline	Daily	Delirium occurrence	Discharge	Follow-up [#]
Investigations				occurrence		
Liver function	*			*		
Electrolytes	*			*		
Full blood count	*			*		
Measures						
Medical file review						
Demographics	*					
Diagnosis	*					
Con meds	*	*	*	*	*	*
Prn medications		*	*			
Specific medications:		*	*	*		*
Anticholinergics,						
corticosteroid and						
benzodiazepines						
CYP1A2 inhibitors						
(quinolones,						
carbamazepine,						
rifampicin,						
fluvoxamine)						
Warfarin						
Vital signs		*	*	*		
Admission data		*				
Preventative care		*	*	*		
non-						
pharmacological						
measures						
Survival					*	*
Falls			*		*	*
Pressure areas			*		*	*
Pneumonia			*		*	*
Length of stay					*	
Health services		†			*	*
utilisation						
In hospital		†	*		*	
resource utilisation						
Patient measures						
Vision	*					
Hearing	*					

	Eligibility	Baseline	Daily	Delirium occurrence	Discharge	Follow-up [#]
AKPS	*	*		*	*	*
Short Blessed Test		*			*	
Insomnia Severity Index		*	Every five days			
Quality of life (EQ- 5D-5L)		*			*	*
Medical assessment	*		*			
Delirium Experience Questionnaire					* (only if delirium occurred)	* (only if delirium occurred)
Clinician assessed						
Toxicity		*	*	*		*
Charlson Comorbidity Index		*				
Sedation (RASS)		*	*			
DRS- R-98	*		Daily for 7 days.	*		
NuDESC	*	*	* each shift			
Delirium Etiology Checklist		*		*		
Carer measure						
Delirium Experience Questions				*		* (only if delirium occurred in participant)
Carer Experience Scale		*		*		*

[#] Measured up to death or 21 days after ceasing study medication (whichever is the shorter period) by weekly phone call.

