8.10 Exit assessments

Participants will be visited in the morning following the last dose of the study intervention prior to discharge (last day of data collection, or when treatment is ceased, if earlier cessation occurs) for collection of exit data. During the visit, the study nurse will take the measures and assessments as outlined in 8.1 Table of study measures and record the visit in the CRF. This visit will also be recorded within the participant clinical file, along with any instructions or changes regarding ongoing management.

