Defined as recall of information (e.g., 3 items presented either verbally or visually) after a delay of about 2 to 3 minutes. When formally tested, information must be registered adequately before recall is tested. The number of trials to register as well as effect of cueing can be noted on scoresheet. Patient should not be allowed to rehearse during the delay period and should be distracted during that time. Patient may speak or nonverbally communicate to the examiner the identity of the correct items. Short-term deficits noticed during the course of the interview can be used also.

- Short-term memory intact
- Recalls 2/3 items; may be able to recall third item after category cueing 1.
- Recalls 1/3 items; may be able to recall other items after category cueing
- Recalls 0/3 items

Nurses Delirium Screening Scale (NuDESC)²

Date today;	/ /	Day of study	(circle one) 1	1 2	3
Date today,		Day of Stady	(Circle Offe)	_	_

Features and descriptions	Features and descriptions SYMPTOM RATING 0 - 2		
Symptom/time period	Midnight – 8am	8am – 4pm	4pm - midnight
DISORIENTATION:			
Verbal or behavioural of not being orientated to time or place or misperceiving persons in the environment			
INAPPROPRIATE BEHAVIOUR:			
Behaviour inappropriate to place and/or for the person e.g pulling at tubes or dressings, attempting to get out of bed when that is contraindicated and the like			
INAPPROPRIATE COMMUNICATION:			
Communication inappropriate to place and/or for the person e.g incoherence, non-communicativeness, nonsensical or unintelligible speech			
ILLUSIONS/HALLUCINATIONS:			
Seeing or hearing things that are not there, distortion of visual objects.			
PSYCHOMOTOR RETARDATION:			
Delayed responsiveness, few or no spontaneous actions/words e.g when patient is prodded, reaction is deferred and/or the patient is unrousable			
TOTAL SCORE (out of 10)			

Any score of 1 or more

- Contact investigator
- Dose modification schedule as per protocol
- Rescue medications as per protocol

GUIDE TO SCORING:

- **0** = Behaviour **not present** during shift/assessment period.
- 1 = Behaviour **present at some time** during shift/assessment period, but **mild**
- 2 = Behaviour **present at some time** during shift/assessment period, and **pronounced**

Insomnia Severity Index (ISI) ⁵

Insomnia Severity Index (ISI)

Please Rate the Current (i.e. Last Week) Severity of your Insomnia Problem(s):

	none < 30 min	mild 30 - 45 min	modarate 45 - 90 min	severe 90 - 120 min	very > 120 min

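### Sleep quality has no ISI at exit, so participants who leave before about Day 6 give no post-baseline score, and the first repeat alone includes pre-dose nights

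*Protocol*

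**What the plan says.** Section 2.2.2 lists as the last secondary objective that melatonin may "provide other symptom benefits in the form of improved sleep quality". The instrument for it is the ISI, a self-completed form reproduced in section 15.1, which begins "Please Rate the Current (i.e. Last Week) Severity of your Insomnia Problem(s".

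The schedule appears in several places, and they agree:

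- Section 6.2 says sleep quality "will be measured using the Insomnia Severity Index at baseline and every 5 days during the admission".
- Section 7.8.4 gives the same interval: "Sleep quality will be measured using the Insomnia Severity Index (ISI) at every 5 days during admission".
- Table 8.1 marks the ISI at baseline and "Every five days"; the cells for delirium occurrence, discharge and follow-up are blank.

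Section 6.2 gives the reason for the spacing: "Sleep quality will require participant involvement, measured every five days only to minimize participant burden".

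Section 8.10 places an exit visit on the morning after the last dose, at which "the study nurse will take the measures and assessments as outlined in 8.1 Table of study measures". Because that table has no ISI under Discharge, the exit visit does not collect one. The same column does include the EQ-5D-5L and the Short Blessed Test.

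On timing, section 5.1 says "Intervention will be commenced within 48 hours of admission". Section 8.8 puts the baseline assessments on Day 1, just before the first dose that night. Treatment runs until delirium, discharge or three weeks, and no minimum stay is set.

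**The concern.** Two features of the schedule weaken objective 5.

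The larger one is the missing exit score. A participant who goes home or leaves the study before the first five-day point contributes nothing after baseline. One who leaves between two five-day points contributes nothing about the last nights on study drug. Having a post-baseline score therefore depends on when discharge and delirium happen. Both occur after randomisation, and sections 2.2.2 (items 2 and 4) name delirium incidence and length of stay as things melatonin may change. A comparison restricted to participants with a repeat ISI is not fully protected by randomisation.

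The smaller one is that a seven-night recall is paired with a five-day interval. The first repeat must reach back to nights before the first dose, which pulls a true difference between arms towards zero at that assessment.

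Both concern data that are not collected or are collected over the wrong nights, so a later analysis plan could only partly compensate.

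**Working it through.** The protocol gives no figure of its own to reproduce here. The check counts nights.

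**Inputs**
- Recall window: 7 nights (ISI form, section 15.1).
- Interval between forms: 5 days (sections 6.2, 7.8.4, table 8.1).
- Baseline on Day 1, first dose that night (section 8.8).
- Maximum treatment: three weeks (section 5.1).

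**Formula.** For an ISI completed in the daytime of study Day d, with dosing every night from Day 1:

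nights after first dose = min(7, d − 1); pre-dose nights = 7 − that number.

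| ISI on Day | After first dose | Pre-dose |
|---|---|---|
| 5 (if the fifth study day is meant) | 4 | 3 |
| 6 (Day 1 plus five days) | 5 | 2 |
| 10 or 11 | 7 | 0 |
| 15 or 16 | 7 | 0 |
| 20 or 21 | 7 | 0 |

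Day 6 is the more natural reading of every five days after a Day 1 baseline. The pre-dose share of the first window is then 2/7 = 29%; on the Day 5 reading it is 3/7 = 43%. The first window that can lie wholly after the first dose needs d − 1 ≥ 7, that is Day 8 or later. In a full three-week stay, one of four repeats (Days 6, 11, 16 and 21) is affected.

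**Overlap.** Seven-night windows five days apart share 7 − 5 = 2 nights.

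**Nights lost at the end.** Take the last form on Day 6 and an exit on the morning of Day 10, one day before the next form. The nights of Days 6, 7, 8 and 9 are not covered: 4 nights.

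**Stay needed for any repeat.** If the first dose falls within 48 hours of admission, study Day 1 is hospital day 1 to 3, so study Day 6 is hospital day 6 to 8. A participant discharged earlier has a baseline score only. The protocol gives no length-of-stay distribution, so the number affected cannot be computed.

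**Delirium.** Section 1.3 reports pilot times to delirium of 2, 2, 9 and 18 days on placebo and 7 days on melatonin. Two of these five cases, both on placebo, came before a first repeat would be due. This shows that the situation arises; it is too few to estimate how often.

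**The case against.** The strongest reply is that the schedule is a stated choice, consistent across sections, made to spare very ill people a form, and that it serves the last of five secondary objectives. That stands: nothing here is a contradiction, and the five-day spacing should remain. It does not explain why the form is left out of a visit at which other patient measures are already taken.

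Other parts of the reply also stand, and they limit the point:

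- A reader might infer that short stays give no sleep score at all. A baseline ISI is scheduled for everyone; only the post-baseline score is missing.
- A reader might infer that objective 5 as a whole rests on contaminated scores. Only the first repeat includes pre-dose nights, and both arms are affected alike. It can weaken a real difference but does not create a false one.
- A reader might turn 4/7 or 5/7 into a statement that the observed difference is 57% to 71% of the true one. That needs every night to count equally in recall and a full effect from the first dose. The form asks for current severity, several items concern the current problem or its daytime impact, and recent nights may weigh more. The documents support no figure.
- A reader might suppose that most participants reach only the first repeat. Without a length-of-stay distribution this cannot be said.
- Stopping study drug does not by itself end collection. Section 5.13 continues secondary outcomes to the end of the admission, so someone with early delirium who stays in hospital may give a later ISI, though its window would include nights off study drug.

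**Conclusion.** The point holds in a narrow form and is minor. The protocol collects no ISI at the end of treatment. Participants who leave before about Day 6 therefore have no post-baseline sleep score, and others lose up to four final nights. Who is missing depends on events after randomisation that the trial expects treatment to influence; the direction and size of any resulting bias cannot be derived from the protocol.

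The first repeat alone covers 2 of 7 pre-dose nights (3 of 7 on the Day 5 reading). These counts assume a daytime form and nightly dosing from Day 1. They count nights and are not an estimate of lost treatment effect.

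The primary outcome and the sample size do not depend on any of this.

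**What to change.** 1. Mark the ISI in the Discharge column of table 8.1, and so include it in the exit visit of section 8.10, for participants able to complete it. Make the matching change in sections 6.2 and 7.8.4. Keep the five-day spacing.
2. Keep the one-week wording of the form unchanged.
3. Record with each ISI how many study nights its window covers, so that windows wholly after the first dose (Day 8 or later, with dosing continued) can be identified.

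Shortening the recall period after baseline is tempting because it would remove the pre-dose nights. It would, however, compare a seven-night baseline with shorter repeats and depart from the form whose properties and cut-off of 8 are cited in section 7.8.4, so it is not recommended.

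The cost is one more 7-item self-completed form at a visit already made, plus one derived field. The gain is partial. An exit form after a very short stay still contains pre-dose nights: on Day 3, min(7, 3 − 1) = 2 nights follow the first dose and 5 precede it. Participants in delirium may be unable to complete the form, so missing scores related to delirium will remain.

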1. Difficulty falling asleep:	c	O	О	0	О
2. Difficulty staying asleep:	o	0	О	0	О
3. Problem waking up too early:	0	0	0	0	0

		none 0	mild 1	modarate 2	severe 3
4.	How SATISFIED/dissatisfied are you with your current sleep pattern?	0	O	О	0
5.	To what extent do you consider your sleep problem to INTERFERE with your daily functioning (e.g. daytime fatigue, ability to function at work/daily chores, concentration, memory, mood, etc.)?	c	O	o	О
6.	How NOTICEABLE to others do you think your sleeping problem is in terms of impairing the quality of your life?	С	С	О	О
7.	How WORRIED/distressed are you about your current sleep problem?	0	0	O	0

Score = {{insomnia.score = 1*insomnia.falling + 1*insomnia.staying + 1*insomnia.waking + 1*insomnia.stafaction + 1*insomnia.interference + 1*insomnia.noticable + 1*insomnia.worried}}

Richmond Agitation-Sedation Scale (RASS) 7

Procedure

Observe patient.

a. Patient is alert, restless or agitated

c. Any movement in response, but no eye contact

Score 0 to +4

2. If not alert, state the patients name and say 'open yours eyes and look at me'

a. Awakens with sustained eye opening and eye contact

Score -1 Score -2

b. Awakens with eye opening and contact, but not sustained

Score -3

3. When no response to verbal stimulation, physically stimulate by shaking shoulder and/or rubbing sternum

a. Patient has any movement to stimulation

Score -4

b. Patient has no response to any stimulation

Score -5

Score	Term	Description
+4	Combative	Overtly combative, violent, immediate danger to star
+3	Very agitated	Pulls or removes tubes or catheters, aggressive
+2	Agitated	Frequent nonpurposeful movement, fights ventilator
+1	Restless	Anxious but movements not aggressive or vigorous
0	Alert and calm	
-1	Drowsy	Not fully alert, but has sustained awakening
-2	Light sedation	Briefly awakens with eye contact to voice
-3	Moderate sedation	Movement or eye opening to voice but no eye contact
-4	Deep sedation	No response to voice, but movement or eye opening physical stimulation
-5	Unarousable	No response to voice or physical stimulation.
	Score	

Delirium Etiology Checklist (DEC) ³

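### The appended Insomnia Severity Index form sums five-option items with no scores and four-option items scored 0–3, and leaves the satisfaction item without a direction, so its total cannot be tied to the quoted cut-off of 8

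*Protocol*

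**What the plan says.** Improved sleep quality is secondary objective 5 (protocol summary and 2.2.2). Section 6.2 says that it "will be measured using the Insomnia Severity Index at baseline and every 5 days during the admission". Section 13.1.2 lists the participant as the person who completes it.

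Section 7.8.4 describes the instrument ("The ISI is a 7 item scale which characterizes the type of sleep problem") and cites its validation in cancer patients, "with a cut-off of 8 having optimal sensitivity and specificity". It gives no score range.

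The form itself is in 15.1, under the same reference 5:

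- Items 1–3 (falling asleep, staying asleep, waking too early) are answered under the heading "none < 30 min mild 30 - 45 min modarate 45 - 90 min severe 90 - 120 min very > 120 min". That is five options, with minutes but no scores.
- Items 4–7 are answered under the heading "none 0 mild 1 modarate 2 severe 3". That is four options with scores.
- Item 4 reads "How SATISFIED/dissatisfied are you with your current sleep pattern" and uses that same four-option heading.
- The total is a plain sum, "1*insomnia.falling + 1*insomnia.staying + 1*insomnia.waking + 1*insomnia.stafaction + 1*insomnia.interference" plus the noticeable and worried items. Every weight is 1 and no item is reversed.

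**The concern.** A summed score can be interpreted only if each option has a known value, each item has a known direction and the total has a known range. The printed form falls short on all three. The options of items 1–3 carry no value. Item 4 pairs a two-way question with a one-way intensity scale: a very dissatisfied participant could tick *severe* (3), meaning severe dissatisfaction, or *none* (0), meaning no satisfaction. The range is not stated, and the two blocks of items have different maxima.

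At stake are the only patient-reported sleep measure in the trial and the reading of any score level against the validation that 7.8.4 relies on. An analysis plan can fix the coding of items 1–3 later. It cannot add an option to a form already completed, or recover what a participant meant on item 4.

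**Working it through.** **Inputs, all from the protocol**

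- Items 1–3: five options, no scores (15.1).
- Items 4–7: four options, scored 0, 1, 2, 3 (15.1).
- Total: unweighted sum of seven items (15.1).
- Cut-off: 8 (7.8.4). No input in the protocol lets this figure be derived, so it cannot be reproduced.

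**Range of the total as printed.** Items 1–3 use the same four words as items 4–7 and add *very*. The natural coding is therefore none = 0 up to very = 4.

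- Minimum: 3 × 0 + 4 × 0 = 0.
- Maximum: 3 × 4 + 4 × 3 = 24.
- Items 1–3 supply 12/24 = 50% of the maximum. With equal maxima on all seven items they would supply 3/7 = 43%.

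**Where 8 falls.** The protocol does not give the range of the validated version, so uniform formats are shown as assumptions only.

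- Printed form, 0–24: 8/24 = 33% of the maximum.
- Seven items scored 0–4, 0–28: 8/28 = 29%.
- Seven items scored 0–3, 0–21: 8/21 = 38%.

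The value 8 lies inside every one of these ranges. The protocol does not say which of them, if any, the cut-off belongs to.

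**Direction of item 4.** If the intended score is x, the opposite reading gives 3 − x, and the total shifts by (3 − x) − x = 3 − 2x.

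- x = 0: +3
- x = 1: +1
- x = 2: −1
- x = 3: −3

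The largest shift is 3 of 24 points, or 12.5% of the range. For example, a participant who answers *mild* on the other six items scores 6 on them. If very dissatisfied, the total is 6 + 3 = 9 on one reading of item 4 and 6 + 0 = 6 on the other.

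**Effect on the comparison of arms.** Suppose a share p of participants read item 4 the opposite way, equally in both arms and unrelated to their true answer. The protocol gives no value for p. With a true arm mean m on item 4, the expected recorded mean is

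(1 − p)m + p(3 − m) = 3p + (1 − 2p)m.

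A true difference d between arms on this item becomes (1 − 2p)d:

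- p = 0: d
- p = 0.10: 0.8d
- p = 0.25: 0.5d

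If d = 0, the recorded difference is also 0 in expectation. The defect therefore creates no false difference between arms. It shrinks a real one on one item of seven and adds scatter to the total.

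**The case against.** **The page may be damaged in extraction.** The tick circles come through as mixed characters, and the Richmond scale table that follows has lost words at its right edge. Clipping there could remove a fifth option from the heading and the rows together, so their agreement does not exclude a loss. This stands as a caution. Against it, both tables are internally consistent (five headings with five marks per row, four with four), and figures were read in both headings. The item 4 problem does not depend on the number of columns.

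**Item 4 has context.** The instruction at the head of the form asks for the severity of the insomnia problem, which points *severe* towards dissatisfaction. That makes one reading more likely, but it does not settle the matter for a participant who answers the question as printed.

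**Unequal maxima are not an error in themselves.** The Short Blessed Test in the same appendix also sums items with different ranges. That is correct. The difficulty here is that no total range is stated and a cut-off is quoted from a validation whose format is not shown.

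**The cut-off is not used.** Section 7.8.4 mentions 8 only as a psychometric property. Sections 6.2, 11.2 and 11.3 define no responder, eligibility rule or analysis by it. This stands and limits the consequence.

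**A reader might infer that items 1–3 could be coded 1–5,** which would raise every total by 3 and carry many participants across 8. The protocol does not support this: the same words are printed with scores starting at 0 for items 4–7. A constant shift would in any case cancel in mean differences between arms.

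**A reader might also infer that sites would score differently.** Nothing shows this. One formula is printed, and section 13.1.4 has all sites enter data through one study interface.

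**Conclusion.** The concern holds in a limited form. As printed, the form gives no scores for the options of items 1–3, uses four scored options for items 4–7, and sums all seven items without stating a range. Item 4 has no anchored direction. On 0–4 coding of items 1–3 the total runs 0–24, and the opposite reading of item 4 moves it by up to 3 points.

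It is tempting to go further and say that the total is incompatible with the cut-off of 8. The protocol does not support that, because the response format and range of the validated version are not given. It shows only that the printed total cannot be tied to the cut-off.

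The consequence is avoidable measurement error and score levels that cannot be interpreted, on a secondary outcome collected in the same way in both arms. It is not bias between arms, and the primary outcome is untouched. The size rests on two assumptions: that the extracted page shows the columns as the sponsor printed them, and that items 1–3 are coded from 0. How many participants would read item 4 the opposite way is unknown. The correction is worth making because it is cheap and cannot be made at analysis.

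**What to change.** 1. Check the source page of 15.1 for a lost column or lost scores.
2. Replace the appended form with the version validated in reference 5, using that version's response scale for all seven items and printing a score on every option.
3. Anchor item 4 from satisfied to dissatisfied, with the score rising towards dissatisfaction, so that the plain sum runs in one direction.
4. State the total range in 7.8.4 beside the cut-off, so that the two can be read together.

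The cost is one appendix and case report form page, with no extra assessment or participant burden. Any forms already completed need a documented recode. For item 4 a recode can set a convention but cannot recover what each participant meant, so those forms should be identifiable in the data.
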